or requesting for the infusion not to have an additive. In this case, or in any adverse event, the pharmacist will unblind the patient and the nurse by revealing which group the patient is in.

Data Storage:

- (1) All data collection sheets will be coded and not include identifying information.
- (2) The enrollment log(s) will be kept by the research team members in their locked BHSF office drawer or filing cabinet. At the end of the study the enrollment logs will be housed in the principal investigator's locked office drawer or filing cabinet. Enrollment logs will be kept separate from data collection. Peripheral intravenous potassium chloride replacement therapy data collection will be sealed in an envelope and placed in the designated 'research' box in the medication room. Then on a weekly basis the envelopes will be collected by a member of the research team and given to the co-investigator ([name]). Data entry into the BHSF password protected computer system will be done by the designated research team member and then all hard copies will be housed in the principal investigator's BHSF locked office or filing cabinet.
- (3) All demographic and chart review data will be given to the co-investigator ([name]). Data entry into the BHSF password protected computer system will be done by the designated research team member and then all hard copies will be housed in the principal investigator's BHSF locked office or filing cabinet.
- (4) At the end of the study, all data will be housed in the principal investigator's locked BHSF office drawer or filing cabinet.
- (5) All electronic data will be password protected on the BHSF computers of the research team.
- (6) All data will only be accessible by the research team.

**Participants:**

Participants will be recruited from one adult acute care hospital (West Kendall Baptist Hospital) within Baptist Health South Florida (BHSF) health system; one of the largest not-for-profit hospital systems in South Florida. Initial screen will occur during the first 24-48 hours of the Medical/Surgical admission. Inclusion criteria: (1) admitted to the Medical/Surgical unit within the last 24 to 48 hours; (2) alert, awake, and oriented times three; (3) aged 21 years old and greater; (4) receiving her or his first peripheral intravenous potassium chloride replacement therapy as ordered by her or his physician or ARNP as part of her or his care and regardless of research; and (5) potassium level of 3.5 mmol/L or less. Exclusion criteria: (1) patients who have been in the Medical/Surgical unit for more than 48 hours; (2) altered mental status defined as not being alert, awake, and oriented times three; (3) patients who have already received intravenous potassium chloride replacement during the current admission and with the current IV access; (4) patients receiving intravenous Potassium replacement therapy through a central line ; and (5) patients that are not ordered potassium replacement by her or his physician as part of their care while hospitalized.

The literature indicates that the rate of phlebitis for IV administration of toxic substances is substantially higher than with non toxic substances (OR = 5.1). We computed the sample size needed in relation to the main objective of comparing the rate of phlebitis in subjects being administered a toxic substance (Potassium IV replacement) to the rate of phlebitis in subjects receiving the same substance but with the addition of 4% sodium bicarbonate additive (to neutralize the toxicity). Using an alpha of 0.05 in a logistic regression assuming the occurrence of phlebitis without 4% sodium bicarbonate additive at 0.15 and a multiple correlation between the covariates of 0.2, a total sample size of 150 (75 patients per group) would have a power of 80% to detect an odds ratio of 5.0.

This sample size will yield an 80% power to detect a difference as little as 1.5 unit on a 10-point rating scale with unequal variances between the two groups, assuming a ratio of 2.75 between the groups' standard deviations in a Satterthwaite t-test at a two-sided 0.05 level of significance. It will also yield a power of 80% to detect an effect size of 0.46 in the length of administration using a t-test with a 0.05 two-sided level of significance. A sample size of 75 per group will also yield 80% power to detect a probability of 0.632 that an observation in the experimental group is less than an observation in the control group for the frequency of changing the IV, the number of nursing interventions and the rates of attrition using Wilcoxon rank-sum test with a 0.05 two-sided significance level. In addition, considering that currently about 85 patients per month receive IV potassium replacement on the Medical/Surgical floor, it is expected that the research team will be successfully able to enroll the needed sample. Although by power analysis a total of 150 participants is needed, in order to control for confounding variables the sample will be 200 (100 in each group).

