## **Tentative Plan for Data Analysis**

Descriptive statistics for demographic and baseline variables will be computed for both groups using frequencies and proportions for categorical variables and means, medians, standard deviations and ranges for numerical variables. To compare the differential rate of phlebitis between the two groups, we will compute the odds ratio (with a 95% confidence interval) using logistic regression. Although the randomization process aims at eliminating the differences between groups, if the groups end up significantly different in baseline variables, those variables will be controlled in the logistic regression. It

is hypothesized that the variances in pain scales will be different between the two groups. Therefore, to compare the pain level between the groups, we plan on using a Satterthwaite t-test. An independent t-test will be used to compare the length of administration per unit of the medication. All other variables will be compared between groups using Wilcoxon rank-sum tests. All tests will be performed at the 0.05 level of significance unless otherwise specified using Stata 12.1 (StataCorp, Texas).

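### The 80% power claimed for phlebitis with 150 patients does not match the inputs as worded; 0.15 may be mislabelled, so inputs and power need reconciling

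*Combined protocol and SAP*

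**What the plan says.** All the sizing text is in the Participants section of the combined protocol and SAP. It starts from a literature finding that phlebitis with toxic infusions "is substantially higher than with non toxic substances (OR = 5.1"), and compares potassium alone with the same infusion "with the addition of 4% sodium bicarbonate additive (to neutralize the toxicity"). The calculation is for a logistic model at alpha 0.05, made "assuming the occurrence of phlebitis without 4% sodium bicarbonate additive at 0.15 and a multiple correlation between the covariates of 0.2", and concludes that "a total sample size of 150 (75 patients per group) would have a power of 80% to detect an odds ratio of 5.0". Neither the sidedness nor the formula is given for this test.

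The next paragraph makes further power claims at the same size and labels them two-sided, for example "an effect size of 0.46 in the length of administration using a t-test with a 0.05 two-sided level of significance". It closes with "Although by power analysis a total of 150 participants is needed, in order to control for confounding variables the sample will be 200" (100 per group). Under Tentative Plan for Data Analysis, the phlebitis comparison is specified as "we will compute the odds ratio (with a 95% confidence interval) using logistic regression".

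**The concern.** The wording ties 0.15 to the control arm. The literature odds ratio is toxic over non-toxic and the additive is meant to neutralise, so an odds ratio of 5.0 implies a fall from 15.0% to 3.4%. With events that rare in the treated arm, 75 per group looks small for 80% power.

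This calculation serves the declared main objective. As written, a reader cannot tell whether the trial was sized for a fall of 11.6 points (15.0% to 3.4%) or 18.1 points (24.0% to 6.0%). Nor can a reader judge the stated reason for going from 150 to 200. The plan says power needs 150 and attributes the other 50 to confounding. If 0.15 really is the control rate, the usual two-sided formulas need roughly 193 to 290 patients, so power alone would use most of those 50, all of them, or more.

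**Working it through.** **Inputs (Participants section).** Rate 0.15; odds ratio 5.0; alpha 0.05; 75 per group; multiple correlation 0.2. The 0.2 could be ignored, read as R (R-squared 0.04) or read as R-squared. It enters by multiplying the sample size by (1 - R-squared), so 75 per group becomes 75, 72 or 60.

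**Sidedness.** It is not stated for phlebitis. The neighbouring claims are labelled two-sided and reproduce that way at 75 per group: effect size 0.46 gives 79.9%, and the Wilcoxon probability of 0.632 needs (1.960 + 0.842)² / (6 × 0.132²) = 75.1 per group. The planned 95% interval also points to two-sided 0.05.

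**Formulas**, with n per group, arm rates p1 and p2, and mean rate p:

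- Two-proportion-type: power = Φ{[|p1 - p2|√n - z√(2p(1 - p))] / √(p1(1 - p1) + p2(1 - p2))}
- Wald: power = Φ{ln 5 / √([1/(p1(1 - p1)) + 1/(p2(1 - p2))]/n) - z}
- Null-variance log-odds (crude for an odds ratio this large): power = Φ{ln 5 / √(2/(n p(1 - p))) - z}

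**Step 1. Inputs as worded, protective direction.** Control odds 0.15/0.85 = 0.1765; divided by 5 = 0.0353; rate = 0.0353/1.0353 = 0.0341. The difference is 0.1159 and the mean rate 0.0920. With n = 75 and z = 1.960:

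- Two-proportion-type: (0.1159 × 8.660 - 1.960 × 0.4088)/0.4005 = 0.506, power 69.3%
- Wald: 1.609/√((7.843 + 30.369)/75) - 1.960 = 0.295, power 61.6%
- Null-variance: 1.609/0.565 - 1.960 = 0.889, power 81.3%

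| Two-sided 0.05, 15.0% vs 3.4% | 0.2 ignored | R = 0.2 | R-squared = 0.2 |
|---|---|---|---|
| Two-proportion-type, N = 150 | 69.3% | 67.5% | 59.5% |
| Wald, N = 150 | 61.6% | 59.8% | 52.3% |
| Null-variance, N = 150 | 81.3% | 79.7% | 72.2% |
| Two-proportion-type, N = 200 | 81.4% | 79.8% | 72.2% |
| Wald, N = 200 | 74.0% | 72.3% | 64.4% |
| Total N for 80%, two-proportion-type | 193 | 201 | 241 |
| Total N for 80%, Wald | 232 | 241 | 290 |

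Exact enumeration without covariates at 75 per group gives 59.6% (Wald), 62.2% (Fisher), 73.5% (Pearson) and 74.2% (likelihood ratio). At the low end, a continuity-corrected calculation with R-squared 0.2 gives 46.8%.

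**Step 2. Same rates, one-sided 0.05, N = 150** (columns in the same order). Two-proportion-type 79.6% / 78.1% / 71.3%; Wald 72.9% / 71.4% / 64.5%.

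**Step 3. Odds ratio applied upward (15.0% to 46.9%), two-sided, N = 150.** Two-proportion-type 99.2% / 99.0% / 97.4%; Wald 98.2% / 97.8% / 95.2%. The stated 80% does not come from this direction.

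**Step 4. 0.15 as the overall rate.** Arm rates with mean 0.15 and odds ratio 5 are 0.2405 and 0.0595, a difference of 0.1809.

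- Two-proportion-type, R-squared 0.2 (n = 60): (0.1809 × 7.746 - 1.960 × 0.5050)/0.4885 = 0.843, power 80.0%. Required N is 119.9/0.8 = 149.9. Both stated numbers are reproduced. At N = 200, power is 90.1%.
- Wald, R = 0.2 (n = 72): 1.609/√((5.475 + 17.857)/72) - 1.960 = 0.867, power 80.7%. Required N is 147.3. At N = 200, power is 90.4%.
- Other pairings miss: two-proportion-type with R = 0.2 gives 86.8%, and Wald with R-squared 0.2 gives 73.3%.

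**The case against.** The strongest reply is that nothing is wrong with the design. One coherent set of inputs returns exactly 150 and 80.0%, which suggests a sound calculation with a mislabelled rate. This largely stands and is why the point is framed as a mismatch. It does need two departures from the plain wording, though: 0.15 as the overall rate, and 0.2 as R-squared rather than as a correlation.

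Second, some calculations reach about 80% with the rate as worded: a one-sided 0.05 test by the two-proportion-type formula (80% or 78% with 0.2 ignored or taken as R), and the null-variance approximation (81% or 80%). This also stands, so it cannot be said that every method falls short. But the neighbouring power claims and the 95% interval point to two-sided, and the null-variance approximation is crude at this odds ratio. If either was used, the plan should say so.

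Third, 200 are to be enrolled. On the control-rate reading this brings two-sided power to 81% / 80% / 72% (two-proportion-type) or 74% / 72% / 64% (Wald), so it helps but does not settle the matter.

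A reader might infer that the trial is underpowered for phlebitis. The documents do not support that: they do not show which rate, formula, covariate value or sidedness was used, and one plausible set delivers the stated power.

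**Conclusion.** The stated inputs and the stated power do not agree under the usual two-sided calculations. Taking 0.15 as the control rate and the effect as protective, 150 patients give about 60-69% (two-proportion-type), 52-62% (Wald) or 60-74% (exact unadjusted), against the 80% claimed. This rests on two-sided testing, which is inferred, and on methods that do not exhaust the possibilities. The claim is recovered with 0.15 as the overall rate, provided that 0.2 is R-squared in the two-proportion-type formula or, approximately, R in the Wald formula.

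It is therefore an inconsistency to be reconciled, not a demonstrated shortfall. It should be fixed because the phlebitis calculation carries the main objective, and the assumed control rate (15% or 24%) affects how a non-significant result would be read.

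**What to change.** The trial statistician should check the original calculation and correct the sizing paragraphs under Participants to match it.

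(a) If 0.15 is the control rate and the test is two-sided: state arm rates of 15.0% and 3.4%, and restate the power by the formula actually used. By the two-proportion-type formula this is about 67-68% at 150 and 80% at 200 with R = 0.2, or 60% and 72% with R-squared 0.2. Withdraw, for phlebitis, the statement that 150 suffices by power analysis. If the test was one-sided, say so and give the two-sided figures as well.

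(b) If 0.15 is the overall rate: label it as the rate across both arms, give arm rates of 24.0% and 6.0%, and state the combination that yields 80% (two-proportion-type with R-squared 0.2, or Wald with R = 0.2). The 80% at 150 can then stay, with about 90% at 200.

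In either case state the formula, whether 0.2 is R or R-squared, the sidedness, and which arm is the numerator of the odds ratio.

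The cost is one check and a few reworded sentences. Enrolment of 200 and the analysis are unchanged. The only downside is a possibly less favourable stated power under (a).

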## **Other Pertinent Information:**

*Standard of Practice for Potassium chloride replacement therapy:* The Physician or ARNP evaluates the Potassium level of the patient and orders potassium replacement therapy for potassium level of 3.5 or below. The amount of replacement of potassium intravenously is determined by the patient's physician or ARNP based on patient's condition and potassium level as standard of practice and the order is provided to the direct patient care nurses and pharmacy. Patients with peripheral IV access may be ordered to receive intravenous potassium replacement therapy of 10 mEq/100 ml Normal Saline bag, ordered as one or multiple doses depending on the potassium level and patient's condition. The peripheral intravenous site is being assessed per protocol for phlebitis once per shift and as needed. During potassium chloride intravenous replacement direct patient care nurses can initiate nursing interventions including but not limited to: changing IV site, slowing rate of infusion, and requesting from the patient's physician or ARNP an order for 4% sodium bicarbonate additive solution.

*Study Procedures covered:* Those participants in experimental group who will receive up to 4 doses of 4% sodium bicarbonate will not be charged for those experimental doses. The Academy of Medical-Surgical Nurses (AMSN) is sponsoring this study and the cost of 4% sodium bicarbonate to Pharmacy will be covered by AMSN.

### *Limitations*

This study has some limitations. Firstly, the sample will include patients in a Medical/Surgical units admitted for various reasons which can result in varying intravenous drug therapy. For this reason participants will be randomized and only those that have been on the unit for 24-48 hours will be approached for enrollment. Secondly, the direct patient care nurses will be assessing phlebitis and pain at IV insertion site which can reduce fidelity of data collection. Therefore, a reliable and valid tool will be used along with initial education and additional education at six months will be provided by the research team.

### *Potential Benefits of the Proposed Research to the Subjects and Others*

While there is no outward benefit to the participant for taking part in the study, the knowledge gained from this study will add to the body of nursing knowledge specific to Medical/Surgical nursing as it relates to intravenous therapy and patient comfort. This study will test how 4% sodium bicarbonate additive could help reduce or prevent phlebitis and pain which is hospital acquired conditions. In addition, it is possible that participants will feel a sense of satisfaction in helping determine if an inter-collaborative pharmacist and nurse-driven prevention strategy can help with reducing the rate of phlebitis and pain at the IV insertion site of patients receiving potassium replacement. If the result of this study is positive, it could be used as evidence that hospital acquired phlebitis could be prevented or reduced with great implications to nursing practice in the decrease of frequency of changing peripheral access, cost-effectiveness and possible harm to the patient.

## **Tentative Plan for Data Analysis**

Descriptive statistics for demographic and baseline variables will be computed for both groups using frequencies and proportions for categorical variables and means, medians, standard deviations and ranges for numerical variables. To compare the differential rate of phlebitis between the two groups, we will compute the odds ratio (with a 95% confidence interval) using logistic regression. Although the randomization process aims at eliminating the differences between groups, if the groups end up significantly different in baseline variables, those variables will be controlled in the logistic regression. It

is hypothesized that the variances in pain scales will be different between the two groups. Therefore, to compare the pain level between the groups, we plan on using a Satterthwaite t-test. An independent t-test will be used to compare the length of administration per unit of the medication. All other variables will be compared between groups using Wilcoxon rank-sum tests. All tests will be performed at the 0.05 level of significance unless otherwise specified using Stata 12.1 (StataCorp, Texas).

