**Significance:**

Hypokalemia, or the low concentration of potassium (below 3.5 mmol/l), is a condition that can result in serious adverse effects including disturbances in cardiac conduction along with muscle, kidney,

gastrointestinal tract, genitourinary tract, respiratory, and endocrine dysfunction (Asmar, Mohandas, & Wingo, 2012; Hemstreet, et al., 2008). Hypokalemia is typically a result of chronic medical conditions such as reduced intake of potassium, chronic diuretic therapy, diarrhea, short bowel syndrome, vomiting and burns. Although potassium can be replaced orally, IV potassium chloride is utilized in patients that need rapid replacement, are showing clinical signs of low potassium, or patients who are unable to orally ingest the replacement. Potassium should always be diluted and slowly administered to reduce the likelihood of pain from inflammation of the vein or phlebitis. (Pharmacology for the Prehospital Professional, 2011). Yet, even at slow rates of 10 mEq/h phlebitis and pain have been reported in 60% of patients (Stephens et al., 1976).

Peripheral venous cannulation (PVC) is a common procedure carried out in hospital to allow rapid and accurate administration of medication (Endacott et al., 2009). In replacing Potassium intravenously, nurses need to have intravenous access. In WKBH 3 South/3 North/4 South Medical-Surgical Telemetry units, nurses often receive orders for Potassium replacement through Intravenous route. The majority of these patients have peripheral intravenous access. The intravenous access is often started in the Emergency Department and continued once the patient is admitted. The peripheral intravenous site is being assessed per protocol for phlebitis once per shift and as needed.

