  - a. Participants enrolled in the control group will receive standard of practice which is intravenous potassium replacement without the 4% sodium bicarbonate additive at the rate ordered by the ordering physician or ARNP for peripheral intravenous potassium chloride replacement therapy which will be part of the care of the patient regardless of research, and based on the WKBH policy of potassium chloride infusion of no more than 100ml/hr. Pharmacist prepares, as standard of practice, each bag of 100 ml normal saline (NS) with 10mEq potassium chloride.

- b. Participants enrolled in the experimental group (4% sodium bicarbonate additive during peripheral intravenous potassium chloride replacement therapy) will receive the additive after pharmacy and/or the designated key personnel ([name]) coordinates the ordering of 4% sodium bicarbonate additive during peripheral intravenous potassium chloride replacement therapy. Pharmacist prepares, when ordered as standard of practice, each bag of 100 ml NS with 10mEq Potassium Chloride and 5 ml of 4% sodium bicarbonate additive, therefore, this practice will be used for the experimental group. The rate of peripheral intravenous potassium chloride replacement therapy will be ordered by the ordering physician or ARNP, for IV potassium chloride replacement therapy which will be part of the care of the patient regardless of research, and based on the WKBH policy of potassium chloride infusion of no more than 100ml/hr.

[figure not shown]
Data Collection:

- (1) Demographics (please see attached) will be collected by the principal investigator or designated key personnel after enrollment of patient.
- (2) peripheral intravenous potassium chloride replacement therapy (please see attached) data collection form: assessment of peripheral IV insertion site for phlebitis, using the VIP tool, and pain, using the Likert 11 point scale will be collected at baseline (prior to any peripheral intravenous potassium chloride replacement therapy), at 15 minutes after infusion started, every hour until peripheral intravenous potassium chloride replacement therapy is complete, and then at completion of replacement.

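### The phlebitis comparison does not separate phlebitis present before the first bag from new phlebitis; if old cases are counted, the odds ratio is pulled toward 1, and the planned baseline-adjustment rule does not correct it

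*Combined protocol and SAP*

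**What the plan says.** The section Tentative Plan for Data Analysis sets the main comparison: "To compare the differential rate of phlebitis between the two groups, we will compute the odds ratio", by logistic regression with a 95% confidence interval. It does not say which VIP score counts as phlebitis, at which assessment, or whether the phlebitis must be new. Baseline variables enter the regression only when the groups turn out to differ significantly on them.

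Methods, Data Collection, item 2 has phlebitis (VIP tool) and pain scored before treatment as well as during and after it: they "will be collected at baseline (prior to any peripheral intravenous potassium chloride replacement therapy").

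Significance describes the catheter: "The intravenous access is often started in the Emergency Department and continued once the patient is admitted".

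Participants lists five inclusion and five exclusion criteria. None concerns the condition of the site. The nearest one excludes earlier intravenous potassium chloride in the current admission through the current access, not an inflamed vein.

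Participants also sizes the trial on phlebitis, "assuming the occurrence of phlebitis without 4% sodium bicarbonate additive at 0.15", and states that "a total sample size of 150 (75 patients per group) would have a power of 80% to detect an odds ratio of 5.0". The section does not say whether the 0.15 refers to new phlebitis only. Planned enrolment is 200, 100 per group.

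**The concern.** A site can be inflamed before the first potassium bag: the catheter may have been placed earlier, and Limitations notes that intravenous drug therapy will vary between participants. The additive cannot prevent phlebitis that is already there. If such cases count as events, they add about the same number to each arm whatever the treatment does, so the odds ratio moves toward 1.

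The plan's only safeguard is adjustment when the arms differ significantly at baseline. That rule addresses chance imbalance. The dilution needs no imbalance: it is present in full when the arms are perfectly balanced, which is when the rule stays silent. At stake are the size of the estimated effect and the power for the objective on which the trial was sized.

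**Working it through.** **Inputs from the documents.** Control phlebitis 0.15, odds ratio 5.0, alpha 0.05, and odds ratio 5.1 for toxic against non-toxic infusions (Participants); 100 per group. **Assumed, because not given:** baseline prevalence b, and the fraction f of baseline cases that persist and are counted.

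**1. Risks implied by the plan.** Control odds = 0.15/0.85 = 0.1765. Experimental odds = 0.1765/5 = 0.0353, so the risk is 0.0353/1.0353 = 0.0341.

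**2. The plan's own figure.** A pooled two-proportion formula with one-sided alpha 0.05 needs 76 per arm, 152 in total, close to the stated 150. Two-sided it needs 97 per arm, 194 in total. Sidedness is a separate matter, so the loss below is measured at the planned 100 per group, two-sided:

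power = Φ{ [d − 1.96·√(2·p̄(1−p̄)/n)] / √([p₁(1−p₁) + p₂(1−p₂)]/n) }, where d = p₁ − p₂ and p̄ is the mean of p₁ and p₂.

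With 0.15, 0.0341 and n = 100: (0.1159 − 0.0801)/0.0401 = 0.893, so power is 0.81.

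**3. Counting baseline cases.** Observed risk in each arm = bf + (1 − bf) × risk of new phlebitis. For b = 2% and f = 1, control is 0.02 + 0.98 × 0.15 = 0.1670 and experimental is 0.02 + 0.98 × 0.0341 = 0.0534. The odds are 0.2005 and 0.0564, giving an odds ratio of 3.55. Power is Φ[(0.1136 − 0.0868)/0.0436], about 0.73.

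The 3.3% row uses the non-toxic rate implied by the plan: odds 0.1765/5.1 = 0.0346, risk 0.0346/1.0346 = 0.033.

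| Baseline prevalence (f = 1) | Observed risks | Odds ratio | Power, all phlebitis | Power, new phlebitis only, n = 100(1 − b) |
|---|---|---|---|---|
| 0 | 0.150 vs 0.034 | 5.00 | 0.81 | 0.81 |
| 2% | 0.167 vs 0.053 | 3.55 | 0.73 | 0.81 |
| 3.3% | 0.178 vs 0.066 | 3.07 | 0.68 | 0.80 |
| 5% | 0.193 vs 0.082 | 2.66 | 0.62 | 0.79 |

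With f = 0.5 the odds ratio is 4.12 at 2% and 3.34 at 5%. Power is then 0.77 and 0.71.

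**4. Does the adjustment rule help?** In 100,000 simulated trials with 100 per arm and b = 5%, a 0.05 test flagged a baseline imbalance in 4.4%. The median odds ratio was 2.60 unadjusted, 2.61 when flagged trials were switched to new phlebitis only, and 4.64 for new phlebitis only in every trial. The last value is below 5.0 because 0.5 was added to each cell. The rule recovers almost nothing.

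**5. If 0.15 and 0.0341 already include baseline cases.** Power against the plan is then unchanged at 0.81. With b = 2%, the risks of new phlebitis are (0.15 − 0.02)/0.98 = 0.133 and (0.0341 − 0.02)/0.98 = 0.014. The new-onset analysis at 98 per arm has power of about 0.89, so it is still the more sensitive one.

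**The case against.** A reader might infer that the plan counts pre-existing phlebitis as an event. It never says so. The sample-size text speaks of occurrence, Potential Benefits speaks of preventing or reducing hospital-acquired phlebitis, and a pre-infusion score is taken. All of this leans toward new events. This objection stands: the dilution is conditional on how the endpoint is read. However, no rule fixes that reading, so the choice could be made after the data are seen.

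A reader might also carry the table to higher prevalences, where the loss looks alarming. The documents do not support that. The plan's own figures imply about 3.3% for non-toxic infusions, so even the 5% row is above what they suggest. Earlier potassium through the current access is excluded. Sites are checked once per shift and as needed, and a site change is a listed nursing action, so some inflamed sites may be replaced first. Other intravenous drugs could raise the prevalence, but no figure is given.

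Full persistence is the worst case, and treating 0.15 as new phlebitis only is an assumption. If the planning figures already include baseline cases, nothing is lost against the stated power.

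Finally, Significance names reduction as well as prevention as an aim. Restricting to clean sites gives up the reduction part for phlebitis, which is a reason to offer the covariate route as an alternative.

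**Conclusion.** The point holds in a limited form. The phlebitis outcome is not tied to the baseline score, no criterion excludes an inflamed site, and the significance-triggered rule cannot correct dilution from balanced cases. If pre-existing cases are counted, the bias is toward no effect and power falls. It does not create false positives, so a positive result would not be undermined on this ground.

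The size is illustrative. It rests on an assumed prevalence of 2% to 5%, on 0.15 and 0.034 being risks of new phlebitis, and on all baseline cases persisting. Under those assumptions the odds ratio falls from 5.0 to between 3.55 and 2.66, and power at 100 per group falls from 0.81 to between 0.73 and 0.62. With half persistence the loss is smaller, and with no baseline phlebitis it is zero. The change is worth making because it costs almost nothing and the new-onset analysis is at least as sensitive under every assumption examined, apart from a loss of at most about 0.02 in power from the smaller denominator.

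**What to change.** State in the analysis plan that the phlebitis outcome is new phlebitis: a VIP score at or above a prespecified cut-off at any assessment after the infusion starts, among participants below that cut-off at baseline. Keep the others in the pain, administration-time, IV-change, nursing-intervention and attrition analyses, and report how many there are per arm.

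Alternatively, keep everyone and prespecify baseline VIP as a covariate in the logistic regression, whatever a baseline significance test shows. If baseline phlebitis always persists, it predicts the outcome perfectly, and this route amounts to leaving those participants out.

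Cost: a sentence or two, including the cut-off that the plan lacks; no new data. A few participants leave the phlebitis denominator, with power of about 0.81 to 0.79 at 2% to 5% prevalence, and the result then applies to sites clean at baseline. The restriction uses a score taken before any potassium, so treatment cannot affect it. Randomisation happens at enrolment, so this also relies on the scoring nurse not knowing the arm; the Enrollment Process section says the nurse is not informed.
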